10.1.2.7 Visit 8 (Week 24 [± 3 days])

- Measure vital signs (blood pressure, heart rate, respiratory rate, body temperature, and weight).
- Call IVRS/IWRS to register visit and obtain treatment kits number.
- Record all concomitant medication use (including but not limited to asthma background controller, reliever, and vaccine); inquire about AEs/SAEs.
- Perform physical examination.
- Perform spirometry:
 - Spirometry must be done at the study site approximately the same time of the day (preferably in the morning, but it could be done at a different time of the day). Spirometry will be performed after a wash out period of bronchodilators according to their action duration, for example withholding the last dose of salbutamol/albuterol or levosalbutamol/levalbuterol for at least 6 hours, withholding the last dose of LABA for at least 12 hours (ultra-LABA like vilanterol should be withheld for at least 24 hours) and withholding the last dose of LAMA for at least 24 hours.
- Assess menstruation status.
- Obtain blood samples for:
 - Hematology (see [Section 9.1.4](#) for details),
 - Serum chemistry (see [Section 9.1.4](#) for details).
- Systemic drug concentration and ADA (see [Section 9.2.2.1](#) for details).
- Total IgE and antigen-specific IgE (refer to [Section 9.2.2.2](#)).
- Obtain urine pregnancy test (dipstick) if female patients are of childbearing potential (who have commenced menstruating).
- Urinalysis (dipstick).
- Dispense and administer IMP:
 - Patients will be monitored at the study site for a minimum of 30 minutes after the injection if patients receive IMP on site,
 - Record observation of a minimum of 30 minutes after the injection monitored by IMP giver if patients receive IMP at home.
- Remind patients and their parent(s)/caregiver(s)/legal guardian(s) to use salbutamol/albuterol or levosalbutamol/levalbuterol as reliever medication as instructed by Investigator.

- Remind patient and their parent(s)/caregiver(s)/legal guardian(s) to continue their stable dose of ICS alone or in combination with a second controller or as adjusted per Investigator's decision.
- Schedule a site visit 12 weeks later (Week 36 \pm 3 days) at approximately the same time of this visit.

10.1.2.8 Telephone contact at Week 28 and 32 (\pm 3 days)

- Record all concomitant medication use (including but not limited to asthma background controller, reliever, and vaccine); inquire about AEs/SAEs; and report in eCRF along with date of phone call.
- Remind patients and their parent(s)/caregiver(s)/legal guardian(s) to use salbutamol/albuterol or levosalbutamol/levalbuterol as reliever medication as instructed by Investigator.
- Remind patient and their parent(s)/caregiver(s)/legal guardian(s) to continue their stable dose of ICS alone or in combination with a second controller or as adjusted per Investigator's decision.

10.1.2.9 Visit 9 (Week 36 [\pm 3 days])

- Measure vital signs (blood pressure, heart rate, respiratory rate, body temperature, and weight).
- Call IVRS/IWRS to register visit and obtain treatment kits number.
Record all concomitant medication use (including but not limited to asthma background controller, reliever, and vaccine); inquire about AEs/SAEs.
- Assess menstruation status.
- Obtain blood samples for:
 - Hematology (see [Section 9.1.4](#) for details),
 - Serum chemistry (see [Section 9.1.4](#) for details).
- Obtain urine pregnancy test (dipstick) if female patients are of childbearing potential (who have commenced menstruating).
- Dispense and administer IMP:
 - Patients will be monitored at the study site for a minimum of 30 minutes after the injection if patients receive IMP on site,
 - Record observation of a minimum of 30 minutes after the injection monitored by IMP giver if patients receive IMP at home.
- Remind patients and their parent(s)/caregiver(s)/legal guardian(s) to use salbutamol/albuterol or levosalbutamol/levalbuterol as reliever medication as instructed by Investigator.

- Remind patient and their parent(s)/caregiver(s)/legal guardian(s) to continue their stable dose of ICS alone or in combination with a second controller or as adjusted per Investigator's decision.
- Schedule a site visit 16 weeks later (Week 52 \pm 3 days) at approximately the same time of this visit.

10.1.2.10 Telephone contact at Weeks 40, 44, and 48 (\pm 3 days)

- Record all concomitant medication use (including but not limited to asthma background controller, reliever, and vaccine); inquire about AEs/SAEs; and report in eCRF along with date of phone call.
- Remind patients and their parent(s)/caregiver(s)/legal guardian(s) to use salbutamol/albuterol or levosalbutamol/levalbuterol as reliever medication as instructed by Investigator.
- Remind patient and their parent(s)/caregiver(s)/legal guardian(s) to continue their stable dose of ICS alone or in combination with a second controller or as adjusted per Investigator's decision.

For Week 48 only

- Remind patient and their parent(s)/caregiver(s)/legal guardian(s) to withhold bronchodilators prior to next study visit when spirometry is scheduled according to their action duration, for example withholding the last dose of salbutamol/albuterol or levosalbutamol/levalbuterol for at least 6 hours, withholding the last dose of LABA for at least 12 hours (ultra-LABA like vilanterol should be withheld for at least 24 hours) and withholding the last dose of LAMA for at least 24 hours.
- Remind patient and their parent(s)/caregiver(s)/legal guardian(s) to withhold the IMP dosing to secure an interval of 14 \pm 3 days prior to next onsite visit (EOT visit) for patients receiving IMP administration q2w at home or 28 \pm 3 days prior to next onsite visit (EOT visit) for patients receiving IMP administration q4w.

10.1.2.11 Visit 10 (Week 52 [\pm 3 days]), End-of-treatment visit

- Measure vital signs (blood pressure, heart rate, respiratory rate, body temperature, weight, height).
- Call IVRS/IWRS to register EOT visit.
- Record all concomitant medication use (including but not limited to asthma background controller, reliever, and vaccine); inquire about AEs/SAEs.
- Perform spirometry:

Spirometry must be done at the study site approximately the same time of the day (preferably in the morning, but it could be done at a different time of the day).

Spirometry will be performed after a wash out period of bronchodilators according to their action duration, for example withholding the last dose of salbutamol/albuterol or

levosalbutamol/levalbuterol for at least 6 hours, withholding the last dose of LABA for at least 12 hours (ultra-LABA like vilanterol should be withheld for at least 24 hours) and withholding the last dose of LAMA for at least 24 hours.

- Perform physical examination.
- Assess menstruation status.
- Perform 12-lead ECG.
- Obtain blood samples for:
 - Hematology (see [Section 9.1.4](#) for details),
 - Serum chemistry (see [Section 9.1.4](#) for details).
- Systemic drug concentration and ADA (see [Section 9.2.2.1](#) for details).
- Total IgE and antigen-specific IgE (refer to [Section 9.2.2.2](#)).
- Archival serum for those patients who have signed a specific Future Use of Specimens informed consent/assent (refer to [Section 9.3](#)).
- Obtain urine pregnancy test (dipstick) if female patients are of childbearing potential (who have commenced menstruating).
- Urinalysis (dipstick).
- Remind patients and their parent(s)/caregiver(s)/legal guardian(s) to use salbutamol/albuterol or levosalbutamol/levalbuterol as reliever medication as instructed by Investigator.
- Remind patient and their parent(s)/caregiver(s)/legal guardian(s) to continue their stable dose of ICS alone or in combination with a second controller or as adjusted per Investigator's decision.
- Schedule a site visit 12 weeks later (Week 64 \pm 1 week) at approximately the same time of this visit.

10.1.3 Post-treatment period (12 weeks)

10.1.3.1 Telephone contact at Weeks 56 and 60 (\pm 1 week)

- Record all concomitant medication use (including but not limited to asthma background controller, reliever, and vaccine); inquire about AEs/SAEs; and report in eCRF along with date of phone call.
- Remind patients and their parent(s)/caregiver(s)/legal guardian(s) to use salbutamol/albuterol or levosalbutamol/levalbuterol as reliever medication as instructed by Investigator.
- Remind patient and their parent(s)/caregiver(s)/legal guardian(s) to continue their stable dose of ICS alone or in combination with a second controller or as adjusted per Investigator's decision.

For Week 60 only:

- Remind patient and their parent(s)/caregiver(s)/legal guardian(s) to withhold bronchodilators prior to next study visit when spirometry is scheduled according to their action duration, for example withholding the last dose of salbutamol/albuterol or levosalbutamol/levalbuterol for at least 6 hours, withholding the last dose of LABA for at least 12 hours (ultra-LABA like vilanterol should be withheld for at least 24 hours) and withholding the last dose of LAMA for at least 24 hours.

10.1.3.2 Visit 11: (Week 64 [± 1 week]), end-of-study visit

- Measure vital signs (blood pressure, heart rate, respiratory rate, body temperature, and weight).
- Call IVRS/IWRS to register EOS visit.
- Record all concomitant medication use (including but not limited to asthma background controller, reliever, and vaccine); inquire about AEs/SAEs.
- Perform physical examination.
- Perform spirometry:

Spirometry must be done at the study site approximately the same time of the day (preferably in the morning, but it could be done at a different time of the day). Spirometry will be performed after a wash out period of bronchodilators according to their action duration, for example withholding the last dose of salbutamol/albuterol or levosalbutamol/levalbuterol for at least 6 hours, withholding the last dose of LABA for at least 12 hours (ultra-LABA like vilanterol should be withheld for at least 24 hours) and withholding the last dose of LAMA for at least 24 hours.

- Assess menstruation status.
- Perform 12-lead ECG.
- Obtain blood samples for:
 - Hematology (see [Section 9.1.4](#) for details),
 - Serum chemistry (see [Section 9.1.4](#) for details).
- Systemic drug concentration and ADA (see [Section 9.2.2.1](#) for details).
- Total IgE and antigen-specific IgE (refer to [Section 9.2.2.2](#)).
- Obtain urine pregnancy test (dipstick) if female patients are of childbearing potential (who have commenced menstruating).
- Obtain urinalysis test (dipstick).

10.2 DEFINITION OF SOURCE DATA

Source data is all information in original records and certified copies of original records of clinical findings, observations, or other activities in a clinical trial necessary for the reconstruction and

evaluation of the trial. Source data are contained in source documents. Source documents are original documents, data and records such as hospital records, clinic and office charts, laboratory notes, memoranda, pharmacy dispensing records, recorded data from automated instruments, etc.

All the data collected in the eCRF should be transcribed directly from source documents. Data downloaded from the study-associated central laboratories, and spirometry will be considered source data.

10.3 HANDLING OF PATIENT TEMPORARY OR PERMANENT TREATMENT DISCONTINUATION AND OF PATIENT STUDY DISCONTINUATION

The IMP should be continued whenever possible. In case the IMP is stopped, it should be determined whether the stop can be made temporarily; permanent IMP discontinuation should be a last resort. Any IMP discontinuation must be fully documented in the eCRF. In any case, the patient should remain in the study as long as possible.

10.3.1 Temporary treatment discontinuation with investigational medicinal product(s)

Temporary treatment discontinuation may be considered by the Investigator because of suspected AEs. Re-initiation of treatment with the IMP will be done under close and appropriate clinical/and or laboratory monitoring once the Investigator will have considered according to his/her best medical judgement that the responsibility of the IMP(s) in the occurrence of the concerned event was unlikely and if the selection criteria for the study are still met (refer to [Section 7.1](#) and [Section 7.2](#)), AE is sufficiently resolved and unlikely to recur after resuming therapy with IMP.

In addition, the following conditions will be causes for temporary treatment discontinuation:

- Infections or infestations that do not respond to medical treatment.
- Any laboratory abnormality that meets temporary treatment discontinuation criteria as per [Section 17.4](#) on Guidelines for management of specific laboratory abnormalities.
- Any administration of live attenuated vaccines (refer to [Section 17.2](#)) during the study period.

Temporary discontinuation may lead to permanent discontinuation after Sponsor's review on a case by case basis.

10.3.2 Permanent treatment discontinuation with investigational medicinal product(s)

Permanent treatment discontinuation is any treatment discontinuation associated with the definitive decision from the Investigator not to re-expose the patient to the IMP at any time during the study, or from the patient not to be re-exposed to the IMP whatever the reason.

In case of permanent treatment discontinuation, the patient follow-up and visits are detailed in [Section 10.3.4](#).

10.3.3 List of criteria for permanent treatment discontinuation

The patients may withdraw from treatment with the IMP if they decide to do so, at any time and irrespective of the reason, or this may be the Investigator's decision. All efforts should be made to document the reasons for treatment discontinuation and this should be documented in the eCRF.

Patients must be withdrawn from the study treatment (that is from any further investigational product or study procedure) for the following reasons:

- At their own request or at the request of their legally authorized representative (legally authorized representative means an individual or judicial or other body authorized under applicable law to consent on behalf of a prospective patient to the patient's participation in the procedure(s) involved in the research).
- If, in the Investigator's opinion, continuation in the study would be detrimental to the patient's well-being.
- At the specific request of the Sponsor.
- In the event of a protocol deviation, at the discretion of the Investigator or the Sponsor.
- Pregnancy (Note: dupilumab should be stopped but patient should be followed up until the outcome has been determined).
- Anaphylactic reactions or systemic allergic reactions that are related to IMP and require treatment.
- Diagnosis of a malignancy during study, excluding carcinoma in situ of the cervix, or squamous or basal cell carcinoma of the skin.
- Any opportunistic infection, such as TB or other infections whose nature or course may suggest an immunocompromised status (see [Section 17.6](#)).
- Serum ALT >3 upper limit of normal (ULN) and total bilirubin >2 ULN (see [Section 17.4](#))
- Serum ALT >5 ULN if enrollment visit ALT is <2 ULN or ALT >8 ULN if enrollment visit ALT is >2 ULN ([Section 17.4](#)).

Any abnormal laboratory value or ECG parameter will be immediately rechecked for confirmation before making a decision of permanent discontinuation of the IMP for the concerned patient.

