9 ASSESSMENT OF INVESTIGATIONAL MEDICINAL PRODUCT

9.1 PRIMARY ENDPOINT

The primary endpoint for this study is the number (n) and percentage (%) of patients experiencing any TEAE (definition see [Section 10.4.1.1](#)) during total study periods.

Additional analyses will describe the number (n) and percentage (%) of patients experiencing any:

- Serious adverse events (SAE) (SAE definition refers to [Section 10.4.1.2](#)).
- Adverse events of special interest (AESI) (AESI definition refers to [Section 10.4.1.3](#)).
- Adverse events related to IMP.
- Adverse events leading to permanent IMP discontinuation.
- Adverse events other than ISR.

Adverse events, including SAEs and AESI, will be collected at any time during study starting from signed consent form. Any new AEs (including worsening AEs) and ongoing AEs (with onset date before the day of enrollment) at enrollment visit (when done on the same day of EOT or EOS of parent study) will be reported in present study. The Investigator will ask the patient and parents how he/she has felt since the last study visit. To assure the continuing safety of patients in this study, an independent DMC will be responsible for reviewing the safety data on a periodic basis throughout the course of the study as outlined in [Section 6.4](#).

The Investigator should take all appropriate measures to ensure the safety of the patients. Notably, he/she should follow up the outcome of SAEs/AESI until clinical recovery is complete and laboratory results have returned to normal or until progression has been stabilized or death. In all cases, this may imply that observations will continue beyond the last planned visit per protocol, and that additional investigations may be requested by the Sponsor.

When treatment is prematurely discontinued, the patient's observations will continue until the end of the study as defined by the protocol for that patient.

In case of any SAE/AESI with immediate notification brought to the attention of the Investigator at any time after the end of the study for the patient and considered by him/her to be caused by the investigational product with a reasonable possibility, this should be reported to the Sponsor.

Adverse events for each patient will be monitored and documented from the time the subject gives informed consent/assent at Visit 1 until the EOS visit, except for:

- Serious adverse events.
- Adverse events that are ongoing at database lock.

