10 STUDY PROCEDURES

The clinical trial consists of 3 periods, using an add-on therapy approach to conventional background asthma controller medications:

- Enrollment (Visit 1 of present study).
- Open-label treatment period (52 weeks; Visits 1-10).

During the open-label treatment period, patients will continue their background therapy dose regimen, as maintained in the parent study or as modified based on Investigator's judgement.

- Post-treatment period (12 weeks; Visit 11).

The study visits occur on the planned dates (relative to the first injection), as scheduled. The visit schedule should be adhered to within ± 3 days in the treatment period and ± 1 week for the remaining study period.

Spirometry should be done at the study site approximately the same time of the day (preferably in the morning, but it could be done at a different time of the day). Spirometry should be performed at visits as detailed in [Section 9.2.1.2](#).

Once every 2 weeks IMP administration must be separated by at least 11 days. Once every 4 weeks IMP administration must be separated by at least 25 days. The treatment period visits occur q2w up to Visit 3 (Week 4), q4w up to Visit 8 (Week 24), and approximately every 12-16 weeks up to the EOS visit as detailed in [Section 8.1.3](#).

Investigational medicinal product can be administrated at home from Visit 2 (Week 2) after approval of Investigator. Patients should be monitored for a minimum of 30 minutes after injections at home. Observations should be recorded in a support document by injection giver and provided to Investigator or delegated during onsite visit. However, if the parent(s)/caregiver(s)/legal guardian(s) or the Investigator decides not to administer IMP at home, the injections can be performed at the study site by way of unscheduled visits. Patients should be monitored at the study site for a minimum of 30 minutes after injections.

At the time of permanent treatment discontinuation, patients will perform the early treatment discontinuation (ETD) visits including early EOT visit and early EOS visit. Early EOT will be performed 2 weeks (with a ± 3 days window) after last IMP injection whenever possible. If the time of decision taken for permanent IMP discontinuation is >2 weeks after last IMP injection, this early EOT visit should be scheduled as early as possible from permanent discontinuation of IMP decision.

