10.3.4 Handling of patients after permanent treatment discontinuation

Patients will be followed-up according to the study procedures as specified in this protocol up to the scheduled date of study completion, or up to recovery or stabilization of any AE to be followed-up as specified in this protocol, whichever comes last. Study Investigators should continue background therapy after treatment discontinuation, as guided by their medical judgement.

Patients who prematurely discontinue the study medication, at the time of permanent treatment discontinuation, patients will perform:

- Early EOT visit: 2 weeks (with a ± 3 days window) after last IMP injection. If the time of decision taken for permanent IMP discontinuation is >2 weeks $+3$ days after last IMP injection, this early EOT visit should be scheduled as early as possible from permanent discontinuation of IMP decision. All the assessments defined for the EOT Visit 10 will be performed during this early EOT,
- Early EOS visit: 12 weeks after early EOT visit with a ± 1 week window. All the assessment defined for the EOS Visit 11 will be performed during this visit.

Patients who discontinue early from treatment may be asked to return to the clinic to have additional ADA samples collected for analysis based on the overall assessment of antibody titers and clinical presentation at the time of discontinuation.

All cases of permanent treatment discontinuation should be entered by the Investigator in the eCRF when considered as confirmed.

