10.6.1 Hypersensitivity

Allergic reaction is a potential risk associated with the administration of most therapeutic mAb.

Allergic reactions may be defined as an immunologically mediated response to a pharmaceutical and/or formulation agent in a sensitized person. Signs and symptoms are often experienced during or shortly after therapeutic administration. Anaphylaxis may represent the most severe form of allergic reactions; refer to [Section 17.5 "Definition of Anaphylaxis"](#), which describes the clinical criteria for the diagnosis of anaphylaxis.

Patients should be monitored for at least 30 minutes after each study-site administered investigational product administration for any signs or symptoms of a hypersensitivity reaction.

Trained personnel and medications should be available to treat anaphylaxis or any severe allergic reaction if it occurs. Furthermore, the patients will be advised, when the IMP is administered at home, to self-monitor for potential signs and symptoms that may suggest a hypersensitive reaction for 30 minutes after administration.

Anaphylactic reactions or systemic allergic reactions that are related to IMP and require treatment must be reported as an AESI (within 24 hours, for further details, see AESI definition in [Section 10.4.1.3](#)) and study medication must be permanently discontinued. Anti-drug antibodies and PK samples will be collected near the onset and resolution of the AESI for any additional analysis.

In case of suspected anaphylaxis or systemic hypersensitivity reaction, sample for ADA should be obtained as close to the time of the event as possible.

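### Protocol 10.3.3 wrongly ends study procedures, as well as the drug, at mandatory treatment discontinuation, against the follow-up that 10.3.4 and other sections require

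*Protocol*

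**What the plan says.** Section 10.3.3 gives ten grounds for permanent discontinuation, from family request to allergic reaction, malignancy, opportunistic infection and raised ALT. The list is introduced by: "Patients must be withdrawn from the study treatment (that is from any further investigational product or study procedure) for the following reasons".

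The text around it says something else:

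- **10.3.2**, directly before: "In case of permanent treatment discontinuation, the patient follow-up and visits are detailed in" Section 10.3.4. This covers every permanent stop.
- **10.3.4**, directly after: "Patients will be followed-up according to the study procedures as specified in this protocol up to the scheduled date of study completion", or to recovery or stabilization of an adverse event if that is later. It schedules an early EOT visit 2 weeks after the last injection with everything done at Visit 10, and an early EOS visit 12 weeks after that with everything done at Visit 11. If the decision to stop comes late, "this early EOT visit should be scheduled as early as possible from permanent discontinuation of IMP decision".
- **Section 10**: "At the time of permanent treatment discontinuation, patients will perform the early treatment discontinuation (ETD) visits including early EOT visit and early EOS visit".
- **9.1**, repeated in **10.4.3**: "When treatment is prematurely discontinued, the patient's observations will continue until the end of the study as defined by the protocol for that patient".
- **10.6.1**, on IMP-related anaphylactic or systemic allergic reactions that need treatment, which are also a 10.3.3 criterion: "study medication must be permanently discontinued", and ADA and PK "samples will be collected near the onset and resolution of the AESI for any additional analysis".

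The Japan substudy adopts 10.3.3 by reference (17.7.2.9.3.3). Its own procedures section (17.7.2.9) schedules the same two early visits, and footnote b of its flow chart asks children who stop to keep attending. The Japan SAP (1.2.1) handles discontinuation before Week 12 with a treatment policy strategy, so it uses data collected after the stop.

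**The concern.** The parenthesis in 10.3.3 is worded as a definition and sits under a *must*. Taken at its word, it makes stopping the drug and stopping all study procedures the same act, for every criterion in the list. Section 10.3.5 is careful to keep withdrawal of consent for treatment apart from withdrawal of consent for follow-up. The parenthesis removes that distinction.

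The phrase matters most for the safety criteria. Allergic reaction, opportunistic infection, marked ALT elevation and pregnancy are adverse events of special interest (10.4.1.3), and cancers diagnosed during the study are listed as medically important events (10.4.1.2). These are the children in whom 9.1 asks the Investigator to follow events to recovery. A site that opens 10.3.3 at the moment of stopping, and acts on its wording, would cancel the visits at which that follow-up takes place.

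**Working it through.** There is no figure in the plan to reproduce. The check has two parts: whether the texts can be reconciled, and what a site would lose per child by following the parenthesis.

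**1. Can the texts be reconciled?** Only if *study procedure* means dosing-related procedures, and nothing in the protocol says so. On its ordinary meaning the phrase conflicts with 10.3.4, Section 10, 9.1, 10.4.3 and 10.6.1. It also fits badly with 10.3 and 10.3.5, which advise keeping the child in the study. Several features show it to be a drafting slip:

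- The heading and the opening and closing sentences of 10.3.3 concern the IMP only.
- The pregnancy item in the same list asks for follow-up after the drug is stopped.
- 10.6.1 and 10.6.3 restate two of the criteria as stopping the product alone.

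**2. What is scheduled after a stop under 10.3.4?**

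- *Decision within 14 + 3 = 17 days of the last dose.* Early EOT is nominally Day 14 (11 to 17). Early EOS is nominally 14 + 84 = Day 98, with a range from 11 + 77 = 88 to 17 + 91 = 108.
- *Decision later, on Day d.* Early EOT is at d or later, and early EOS nominally at d + 84 or later. For a 300 mg q4w child whose stop is decided when the next dose is due, d = 28 and early EOS is at about 28 + 84 = Day 112 or later.
- Section 10 and 17.7.2.9 put the threshold at 2 weeks without the 3 days. This does not change the counts below.

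**3. What remains of the treatment-emergent period?** In the full analysis set (Protocol 11.4.3.1; main SAP Table 3) it ends 14 weeks = 98 days after the last dose for q2w, and 16 weeks = 112 days for q4w. If the stop is decided at the next due dose, 98 − 14 = 84 days (q2w) or 112 − 28 = 84 days (q4w) are still to run. Under the parenthesis no study visit would fall in them.

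**4. Which scheduled assessments are lost?** ECGs are at Visit 1, EOT and EOS (Protocol 9.1.3; main SAP 2.1.4.5); in Japan they are at screening, EOT and EOS (17.7.2.8.3.4). ADA samples are at Weeks 0, 12 and 24, EOT and EOS (main SAP 2.1.6; Japan SAP 3.6.1.2).

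| Per child | Under 10.3.4 | Under the parenthesis |
|---|---|---|
| Full visits after the stop | 2 | 0 |
| Scheduled post-dose ECGs, stopped before Week 52 | 2 | 0 |
| Scheduled post-dose ADA samples, stopped before the Week 12 visit | 2 | 0 |

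**5. How would the analysis treat the child?** The ADA population needs at least one post-dose ADA result (Protocol 11.3.4), so a child with none drops out of it. Both SAPs (main SAP 2.2; Japan SAP 5.2) class a child not assessed at the last planned visit as lost to follow-up.

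**The case against.** The strongest reply is that the protocol already answers the question. The sections immediately before and after 10.3.3 give the right rule, Section 10 repeats it, and a site would have to prefer one parenthesis to all of them. That stands as to intent. A reader might infer that the protocol directs a loss of follow-up; read as a whole, it does not. It does not rescue the wording, because a contradictory *must* in the section consulted at the time of stopping is still an error.

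Two further points narrow the consequences, and both stand:

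- A reader might infer that an early stopper would have no post-dose ECG at all. Only the scheduled ones are lost. Unscheduled ECGs may exist, and the SAPs include them (main SAP 2.4.5.5 and 2.5.4; Japan SAP 5.4).
- A reader might infer that every child stopped before Week 12 leaves the ADA population. Protocol 9.2.2.1.1 calls for samples near the onset and resolution of any SAE, and of allergic reactions related to the IMP that need treatment. Several of the safety criteria would therefore trigger a sample at onset. The child drops out only if no such sample was taken.

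The last point concerns the remedy. A bare deletion would leave the item on continuation being harmful to the child under a lead-in that covers the product only. Section 10.3.4 would then require both visits, while 10.3.5 describes withdrawal by family decision. The Investigator would have no explicit route to omit a procedure that would harm the child. This is right, and the fix below allows for it.

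**Conclusion.** Section 10.3.3 is wrong as written and should be corrected. It is an erroneous operative phrase that creates a risk of lost safety follow-up; it is not a deliberate design choice. Per child, the risk is two full visits, with the ECG and ADA losses tabulated above. These counts assume that a site follows the parenthesis literally and that no unscheduled or event-driven assessment fills the gap.

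No study-level effect is established. The documents do not say how many children would be affected. A reader might infer that the percentage of patients with any treatment-emergent event would be understated, or that the Japan Week 12 confidence interval would be distorted. Neither can be derived from the documents. What can be said for Japan is that its treatment policy strategy needs post-discontinuation data, and the inherited phrase works against collecting them.

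**What to change.** In the lead-in to 10.3.3 delete *or study procedure*, leave the list of criteria unchanged, and add:

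*Follow-up after permanent treatment discontinuation is per Section 10.3.4, except where consent for follow-up is withdrawn (Section 10.3.5) or the Investigator judges that a given procedure would be detrimental to the patient.*

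The first exception protects a family that wants to stop everything. The second keeps the Investigator able to spare a child a harmful procedure. The Japan substudy inherits the correction through 17.7.2.9.3.3.

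The cost is one wording change in a protocol amendment. It needs IRB/IEC approval before use, health-authority submission where local rules require it, and the Investigator's signature (Sections 12.3 and 15). No visit or procedure is added, because 10.3.4 already schedules them.
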